2.14 Adverse Event Recording

All data captured must be supported by the Investigator's timely assessment and documentation of the adverse event in the case report forms or source documents. All documented adverse events will be reviewed by the Sponsor or designee to determine whether the adverse event meets

regulatory reporting requirements and to ensure timely adverse event reporting to meet local and global regulatory requirements. All adverse events must be followed until their resolution.

Biopsies

Complication with biopsies can include pain, redness, swelling, infection, bleeding, scarring and skin texture irregularities.

Lidocaine

1% lidocaine (Lidocaine) Injection with or without Epinephrine

You may experience pain and numbness at the site of the injection. You may also experience redness, rash, infection, skin damage or nerve damage at the site of the injection. You may experience temporary loss of sensation and muscle function at the site of injection.

Lidocaine with epinephrine contains the preservative sodium metabisulfite which may cause allergic-type reactions including anaphylactic symptoms and life-threatening or less severe asthmatic episodes in certain susceptible people.

Adverse Events Pertaining to Surgical Marker:

Using surgical marker has minimal risks and may produce effects on the body such as redness or a rash. Markings may remain visible for a few days or may be removed with alcohol.

3.0 RISK MANAGEMENT

The Investigator in this clinical trial has been invited to participate based on his/her previous experience with the use of the system and/or similar systems and industry experience. Experience with biopsies is the most critical element in managing subject risk in this trial.

In addition, as with any study, there is a risk of bias. Objective evaluation methods will be used. The value of the compensation to the clinical investigator for conducting the study is not influenced by the study outcome.

All other known risks will be disclosed to the subject via the informed consent process. Since this is an elective procedure and the subjects are volunteers, it can be assumed that their signature on the informed consent is indicative of their agreement to accept the risks involved.

The risks to the subjects who participate in this study are the same as those for most subjects undergoing biopsies when enrolled in a non-ablative radiofrequency study.

4.0 MONITORING PROCEDURES

The Sponsor Standard Operating Procedure (SOP) for monitoring the investigative site will be followed. The sponsor will train the site following sponsor SOP's and may be present at initiation of treatment. The sponsor will also monitor the site periodically. The Investigator/Institution will permit trial-related monitoring, audits, IRB/IEC review, and regulatory inspections by providing direct access to source documents. The sponsor may request intermediate data following each visit

to evaluate treatment progress. Case Report Forms will be reviewed for current data and Regulatory Binders will also be reviewed for correct documents. The sponsor will collect data at the end of the follow up period. The sponsor will list the study on clinicaltrials.gov when required by FDA regulations.

The monitoring plan for this study is outlined in the Cynosure Monitoring Plan.

ASSIGNED CLINICAL RESEARCH MONITOR:

Monitor #1

Name: [name]

Institution: Cynosure, LLC

Address: [name]

5.0 CONSENT MATERIALS

Forms and informational materials which are provided to the subject during the informed consent process are listed below:

Form/Informational Material Description
Post Treatment Instructions
Informed Consent Form

7.0 OTHER INSTITUTIONS

If a part of the study is conducted by an institution that has not previously been identified within the Investigational plan each institution's contact information will be documented below;

No other institutions will be part of this study.

8.0 ADDITIONAL RECORDS AND REPORTS

If this is an IDE study, additional records and reports will be maintained on the investigation in addition to those prescribed in 21 CFR 812 sub-part G. If this is a non-IDE study, the study summary will be maintained on the investigation and may include those prescribed in 21 CFR 812 sub-part G.

Additional Records and Reports:

Report	Submit To	Description/Constraints
N/A	N/A	This is a non-IDE study; no additional records or reports will be maintained.

9.0 SUBJECT WITHDRAWAL

The subject is free to withdraw from this study at any time. The subject must inform the Investigator immediately if they intend to withdraw. To terminate the subject's participation in this study, they must contact the Investigator at the contact information listed on page one of the informed consent form. They will be asked to come to the study clinic or Investigators office to complete a final follow up visit and may be asked to perform end of study procedures. Their decision to participate in this study or to withdraw from this study will not influence the availability of their future medical care and will involve no penalty or loss of benefits to which they are otherwise entitled.

The Investigator in charge of the study can remove the subject from this study without their consent for any reason, including, but not limited to:

- His/her judgment that any condition or circumstance may jeopardize their welfare or the integrity of the study.
- Their failure to follow the instructions of the Investigator(s).
- If the study is stopped by the sponsor and/or Investigators participating in the study prior to completion.

Data collected prior to withdrawal will be used in data analysis but after withdrawal no further data will be collected.

10.0 PHOTOGRAPHY

Standardized photography may be taken of the biopsy site. Photographs will be taken with an appropriate high-resolution digital camera. Camera settings (lighting, distance, background, polarization, etc.) will be reproduced at each visit, so that photographs are suitable for comparison. Photographs will be taken of the treatment area for study purposes. If the subject does not wish to have their photographs taken, they cannot be in the study.

11.0 ADVERSE REACTIONS DEFINITIONS AND REPORTING REQUIREMENTS

All adverse events that occur, starting from the time of the first treatment, will be recorded in the source documents and Case Report Forms (CRF).

Adverse Events (AE) occurring will be captured and followed until the condition resolves, stabilizes, is otherwise explained, or the subject is lost to follow-up. Subjects will be instructed that they may contact the Investigator at any time throughout the course of the study.

The Investigator and/or designated study staff will review each event and assess its relationship to the study device (not related, unlikely, possible, probable, and highly probable). The following definitions will be used for rating relationship to the TempSure™ treatments:

- Not related – The event is clearly related to other factors such as the subject's clinical state, therapeutic interventions, or concomitant medications administered to the subject.
- Unlikely – The event was most likely produced by other factors such as the subject's clinical state, therapeutic interventions, or a concomitant medication administered to the subject; and does not follow a known response pattern to the investigational product.
- Possible – The event follows a reasonable temporal sequence from the time of investigational product administration; **and/or** follows a known response pattern to the study sampling sessions; **but** could have been produced by other factors such as the subject's clinical state, therapeutic interventions, or concomitant medications administered to the subject.
- Probable – The event follows a reasonable temporal sequence from the time of investigational product administration; **and** follows a known response pattern to the investigational product; **and** cannot be reasonably explained by other factors such as the subject's clinical state, therapeutic interventions, or concomitant medications administered to the subject.
- Highly Probable – The event follows a reasonable temporal sequence from the time of investigational product administration; **and** follows a known response pattern to the investigational product; **and** cannot be reasonably explained by other factors such as the subject's clinical state, therapeutic interventions, or concomitant medications administered to the subject; **and** either occurs immediately following investigational product administration, **or** improves on stopping the investigational product, **or** reappears on repeat exposure, **or** there is a positive reaction at the application site.

Each adverse event reported will be graded on a 3-point severity. Using the following definitions for rating severity will be used:

- Mild – easily tolerated, causing minimal discomfort, and not interfering with normal everyday activities.
- Moderate – sufficiently discomforting and may interfere with normal everyday activities.
- Severe – incapacitating and/or preventing normal everyday activities.

A Serious Adverse Event (SAE) is any adverse device experience that results in any of the following outcomes: death, a life-threatening adverse device experience, in-patient hospitalization or prolongation of hospitalization, a persistent or significant disability/incapacity, or a congenital anomaly/birth defect. Important medical events that may or may not result in death, be life-threatening, or require hospitalization may be considered a serious adverse device experience when, based upon appropriate medical judgment, they may jeopardize the subject or subject may require medical or surgical intervention to prevent one of the outcomes listed in this definition

If any of the above adverse events are serious as defined by the FDA Code of Federal Regulations (CFR), Title 21, special procedures will be followed. All serious adverse events will be reported within 24 hours of acknowledgment to the Sponsor whether or not the serious events are deemed sampling session-related. All serious event reporting will adhere to 21 CFR part 812 and the IRB will be notified accordingly.

The SAE information will be entered into the database and a desk copy of the complete SAE report will be submitted to the study file.

Adverse events, whether serious or non-serious, will be followed until the condition is resolved, stabilized, otherwise explained or the subject is lost to follow-up. Adverse events will be captured throughout the study and where appropriate, medical tests and examinations will be performed to document the resolution of event(s). Outcomes may be classified as resolved, improved, unchanged, worse, fatal, unknown or lost to follow-up. Following the resolution of any study-associated adverse events there will be no further adverse event reports for that subject.

Reporting Adverse Events:

Report	Submit To	Description/Constraints
Adverse Events, Unanticipated Adverse Device Effect	IRB and Sponsor	If an unforeseen complication is determined to be an unanticipated adverse device effect, the investigator's report must be submitted within 10 working days after the investigator first learns of the effect.
Serious Adverse Events	IRB and Sponsor	The sponsor must be notified within 24 hours of serious adverse events. The IRB must be notified within 10 working days of serious adverse events as defined by FDA guidelines.

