1.0 PURPOSE

1.1 Name and Intended Use

The purpose of this study is to evaluate histological results of the treatments with the TempSure Firm handpiece on the flanks performed in the CYN20-FIRM-LIPO study.

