2.0 PROTOCOL

2.1 Protocol Methodology and Analysis

Methodology:

Subjects are to be enrolled in this clinical study if they have completed their participation in the CYN20-FIRM-LIPO study. Up to 10 subjects will be enrolled at up to 4 study centers. Subjects will receive 2 biopsies, 1 biopsy in the treatment area on the flank and 1 biopsy on the contralateral side to serve as a control.

Analysis:

Upcoming generations are proving to have an interest in non-ablative aesthetic treatments and will drive demand for innovated products, procedures, and practice design.³ Due to this shift in patient base, practices need to evolve to adapt to the newer generational ideologies. There have been rapid advances in RF technology over the past few years and the nonsurgical treatment using this energy source offers great promise to our aging population.⁴ Radiofrequency technology for the treatment of abdominal wrinkles needs to be further investigated to optimize treatment parameters for safe and effective non-ablative aesthetic treatments.

Relevance:

Over time, skin structure degrades due to a variety of internal and external conditions. As enzymes break down collagen and elastin, skin loses its suppleness and becomes loose. UV exposure, diet, and smoking among other behaviors all contribute to the skin becoming lax. Body wrinkles, particularly on the abdomen, are a sign of aging and are also a prevalent concern with postpartum women or subjects who have lost weight. It is estimated that adult skin loses approximately 1% of its dermal collagen content on an annual basis due to increased collagen degradation and decreased collagen synthesis.² Radiofrequency, ultrasound, non-ablative fractional technology, and ablative technology have all been used to varying degrees of success. The limitations of current products on the market include different side effect profiles and modes of administration.

Testability:

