2.5 Informed Consent Process and Enrollment

Subjects will be asked to review the post treatment instructions prior to signing the informed consent form and their involvement in the study. Subjects will be informed of standard COVID-19 procedures that adhere to federal and state guidelines at this time. Subjects will be de-identified through their subject identification number, which will be stored in a secure location. Subject identification numbers will be generated chronologically and assigned only to subjects who have met all the study selection criteria and have signed the informed consent form. The informed consent will be obtained prior to a subject's involvement in any study related procedures. A subject will be considered enrolled in the study once they have signed the informed consent form.

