2.12 Schedule of Visits and Procedures

	Visit #1	Visit #2 (optional)
Procedure	Biopsy	Follow Up 1 Week Post Biopsy (7-10 Days)
Pregnancy Verification*	X	
Biopsy	X	
Suture Removal		X
Photographs	X	X
Adverse Events Assessment	X	X

*Pregnancy verification required before biopsy only for women of childbearing potential.

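### Section 11.0 ties the adverse-event start, the serious-event definition and the causality rating to a device treatment that this biopsy-only study does not give, and contradicts other parts of the Protocol

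*Protocol*

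**What the plan says.** - **Start of recording.** Section 11.0: "All adverse events that occur, starting from the time of the first treatment, will be recorded in the source documents and Case Report Forms (CRF"). Later the same section says that events are captured for the duration of the study.
- **Serious events.** Section 11.0: "A Serious Adverse Event (SAE) is any adverse device experience that results in any of the following outcomes". The sentence on important medical events uses the same device term. The next paragraph refers to events that are serious under Title 21 of the CFR. It asks for notice to the sponsor within 24 hours whether or not the event is related to a sampling session, a term the Protocol never defines.
- **Causality.** Section 11.0 rates each event's relationship to the study device, with five categories worded for the TempSure treatments.
- **What this study does.** Section 1.1 describes the object of evaluation as "treatments with the TempSure Firm handpiece on the flanks performed in the CYN20-FIRM-LIPO study". Section 2.1: "Subjects will receive 2 biopsies, 1 biopsy in the treatment area on the flank", with a second on the opposite side as control. Section 2.7 has a local anesthetic injected first. The Section 2.12 table has a biopsy visit and an optional follow-up, with "Adverse Events Assessment" marked at both and no treatment visit.
- **Consent.** Section 2.5: "The informed consent will be obtained prior to a subject's involvement in any study related procedures". A subject counts as enrolled on signing.
- **Known risks.** Section 2.14 lists complications of the biopsy, the lidocaine injection and the surgical marker. It says that the preservative in lidocaine with epinephrine "may cause allergic-type reactions including anaphylactic symptoms and life-threatening or less severe asthmatic episodes" in susceptible people.

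**The concern.** The safety section reads as if written for a study that applies the device. Here the device was used earlier, under another protocol, and the procedures that can cause harm are the injection and the punch. Three safety rules therefore refer to something that does not happen in this study: when recording starts, what counts as serious, and what an event is rated against.

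What is at stake is consistency and completeness of safety data. Sites could use different start dates, so event listings might not be comparable. A serious reaction to a study procedure could be argued out of the definition that leads to 24-hour notice. A plainly biopsy-related event would be entered as unrelated, with nowhere to record its actual cause.

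**Working it through.** There is no figure to reproduce, because the point rests on wording. The check sets the sections side by side.

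**1. Start of recording.** The trigger is "starting from the time of the first treatment". Two meanings are possible.

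- *TempSure treatment.* Section 11.0 itself speaks of TempSure treatments when it introduces the causality scale, and Section 1.1 places those treatments in the parent study. Under Section 2.3 a subject enters after completing that study, at most 6 months earlier. Recording would then open before this study's consent by g + d. Here g is the gap after completion (0 to 6 months), and d is the time from first TempSure treatment to completion of the parent study. The Protocol does not give d, so the total cannot be computed. Stated participation in this study is up to 1 month (Section 1.3).
- *Biopsy.* Section 2.6, on pre-biopsy procedures, times the pregnancy test relative to the treatment, which there can only mean the biopsy. Recording would then open at Visit 1, after consent. Events between consent and biopsy are lost; the Protocol does not fix that interval, and it may be short. If the punch itself is the start, a reaction to the marker (Section 2.6) or to the anesthetic injected before the punch (Section 2.7) could also come too early to count. Both are named sources of harm in Section 2.14.

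Neither meaning agrees with enrollment at signature (Section 2.5) together with capture for the whole study (Section 11.0). The first starts too early and the second too late.

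**2. Serious events.** Section 11.0 can be taken in order:

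- The defining sentence covers device experiences only.
- The important-medical-events sentence widens the outcomes but keeps the device limit, so it does not bring in a biopsy or lidocaine event.
- The Title 21 sentence brings in a second standard, without saying which governs if the two differ.
- The 24-hour rule drops the relatedness test, but for events already classed as serious. Its mention of sampling sessions suggests that procedure-related events were meant to be covered, which the definition does not do.

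Taking the reaction that Section 2.14 describes ("may cause allergic-type reactions including anaphylactic symptoms and life-threatening or less severe asthmatic episodes"): by outcome it is serious, by the definition's opening words it is not a device experience, and by the 24-hour rule it seems intended for notice. Two sites could classify it differently, and each could cite Section 11.0.

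**3. Causality.** An infection at the punch site would be rated against a device last used in the parent study. The scale treats other therapeutic interventions as alternative causes, so the natural rating is not related or unlikely. The only trace of this study's procedure is a reference to sampling sessions inside the category for possible relationship; the two higher categories refer to the investigational product alone. There is no rating for relationship to the biopsy or the anesthetic.

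**Exposure.** Up to 10 subjects × 2 biopsies = up to 20 biopsies, each preceded by local anesthetic, at up to 4 centers (Section 2.1).

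**The case against.** The strongest reply is that the rest of the Protocol shows what was meant. Section 2.6 uses treatment for the biopsy, Section 2.8 calls the biopsied skin treated, and Section 5.0 lists post-treatment instructions as consent material for a study with no other procedure. Section 2.12 schedules event assessment only at this study's visits. Nothing asks sites to transcribe parent-study events. On seriousness, the Title 21 reference, the 24-hour rule and the reporting table in Section 11.0, which has no device qualifier for serious events, all favor reporting. Section 2.14 has the sponsor or its designee review every documented event for reportability.

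Much of this stands, and it rules out two stronger readings. A reader might infer that recording definitely opens in the parent study. The documents do not support that, because the word is used both ways. A reader might also infer that serious biopsy or lidocaine events are definitely excluded from expedited notice. That is not supported either, because other sentences point toward including them. Nor can one say how far the window would be lengthened, or that parent-study events were already reported there, since the Protocol gives neither the parent study's duration nor its event reporting.

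What the reply does not remove is the contradiction. The biopsy meaning still conflicts with capture for the whole study. The sponsor's review reaches only events that have been documented. The broader sentences on seriousness stand beside a narrower definition with no rule of precedence. The reply does not address causality at all.

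**Conclusion.** The point holds as one of ambiguity and internal contradiction. The start of recording has two readings, and neither fits Sections 2.5 and 11.0 together. The serious-event definition is narrower than the reporting rule that depends on it, so a site could reasonably leave out a serious biopsy or anesthetic event. The causality scale has no rating for either of this study's own interventions.

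All subjects are affected (up to 10, at up to 4 centers). How many events would be misplaced or misclassified cannot be estimated from the Protocol. The conclusion assumes only that sites apply Section 11.0 as worded and receive no clarifying CRF instruction outside the Protocol. The sole objective, histological response, is unaffected. The wording should still be corrected because it governs the trigger for expedited safety reporting and costs little to change.

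**What to change.** Amend Section 11.0 and reconcile it with Sections 2.5, 2.6, 2.12 and 2.14:

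1. Start adverse-event recording at signature of this study's consent form. Keep Section 11.0's existing rule for following events until they resolve or stabilize.
2. Define a serious adverse event as any adverse event that meets a listed outcome, regardless of cause. Remove the device limit from the list of outcomes and from the important-medical-events sentence as well. Define sampling session or replace it with the biopsy procedure, and state how the Title 21 reference relates to the definition.
3. Rate relationship separately to the biopsy, to the local anesthetic and to the earlier TempSure treatment.

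The cost is one protocol amendment with IRB approval, and a small CRF change for the start date and the added relationship items. No visit or procedure is added, and the histological evaluation does not change.

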2.7 Biopsy Procedures

- Biopsy subjects will receive 2 biopsies, 1 in the treatment area and 1 on the contralateral side of the treatment area to serve as a control.
- A local anesthetic, such as lidocaine, will be injected to the area prior to biopsy.
- A 2 mm or 3mm punch biopsy (based on Physician assessment) will be taken.

- Sutures may be used to close the incision site.

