2.9 Follow Up

- The subject may be asked to attend a 1 week (7-10 days) post biopsy follow up visit to remove the sutures.

- Photographs may be taken, and adverse events will be documented at this follow up visit.

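### Section 11.0 ends adverse-event reports for a subject once study-associated events resolve, which conflicts with capture throughout the study and assessment at follow-up

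*Protocol*

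**What the plan says.** The last sentence of the closing text paragraph of Protocol Section 11.0, just above the reporting table, reads: "Following the resolution of any study-associated adverse events there will be no further adverse event reports for that subject".

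Four other statements set the scope of adverse-event collection:
- Section 11.0, same paragraph: "Adverse events will be captured throughout the study".
- Section 11.0, opening sentence: "All adverse events that occur" are to be entered in the source documents and CRF.
- Section 2.9, on the one-week visit: "adverse events will be documented at this follow up visit".
- Section 2.12: the row "Adverse Events Assessment" is marked at Visit 1 and at Visit 2, the latter being optional.

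On the procedure itself, Section 2.7 says: "Biopsy subjects will receive 2 biopsies, 1 in the treatment area and 1 on the contralateral side of the treatment area". Section 2.14 lists the expected complications.

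The causality scale in Section 11.0 has five grades and rates relationship to the TempSure treatments. By Section 1.1 these were given in the earlier study. The response-pattern criterion in *Possible* refers to sampling sessions. In *Unlikely*, *Probable* and *Highly Probable* it refers to the investigational product.

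**The concern.** A rule that closes reporting for a subject differs from a rule that closes follow-up of an event. Each subject has two biopsy sites, each with an injected anaesthetic, so a second, unconnected event after a first has resolved is an ordinary possibility. If a centre applies the sentence as written, such an event may not be reported. Another centre that follows Sections 2.9 and 2.12 would report it. With up to 4 centres, the safety listing could then rest on two different rules.

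The wording of *Possible* raises a smaller question of attribution. If sampling sessions means the biopsies, an event that merely looks like a biopsy complication satisfies a criterion for relatedness to the device.

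**Working it through.** The plan gives no figure to reproduce on this point. The check compares the text and adds a few counts.

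**1. Unit of the rule.** The stop sentence names the subject. Follow-up of a single event to resolution is already settled elsewhere: in the second paragraph of Section 11.0, in the first sentence of the paragraph that holds the stop, and in Section 2.14. If the sentence only meant that a resolved event needs no more follow-up reports, it would largely repeat these. Its own wording adds something different, a stop at subject level.

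**2. Cases.** Let A be a study-associated event and B a later, different event in the same subject.
- No study-associated event has occurred before B: the stop is not triggered.
- A is still open when B starts: the sentence uses the plural, and if it means that all such events must have resolved, the stop is not yet triggered.
- B starts after A and all other study-associated events have resolved: the stop sentence says no report, while the other statements require capture. This is the conflict.
- As above, but the subject does not attend the optional Visit 2: Sections 2.9 and 2.12 no longer bear on it, but the two statements in Section 11.0 ("Adverse events will be captured throughout the study" and "All adverse events that occur") still do.
- B is serious or an unanticipated device effect: the reporting table requires notice on its own terms (sponsor within 24 hours and IRB within 10 working days for serious events; 10 working days for unanticipated effects).

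**3. Can the third case arise?** Section 2.14 describes a short-lived anaesthetic effect: "You may experience temporary loss of sensation and muscle function at the site of injection". It also says: "Complication with biopsies can include pain, redness, swelling, infection, bleeding, scarring and skin texture irregularities". Suppose that numbness is recorded as an adverse event, is classed as study-associated (the protocol does not define the term) and resolves. A later non-serious infection or bleed at either site then falls under the stop. Each of these steps is an assumption.

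**4. Bounds.** Section 2.1 allows up to 10 subjects with 2 biopsies each: 10 × 2 = 20 sites at most. Section 2.12 schedules 1 + 1 = 2 adverse-event assessments, the second optional. The protocol gives no event rates, so the number of affected events cannot be estimated.

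**5. Causality wording.** Of the five grades, four use a response-pattern criterion. Three of the four refer to the investigational product and one, *Possible*, to sampling sessions. Its two positive criteria, timing and pattern, are joined by and/or, so the pattern alone can satisfy that part of the definition. Section 2.12 schedules no tissue sampling other than the biopsies, so biopsies are the likely meaning, although the term is undefined.

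**The case against.** The strongest reply separates recording from reporting. The statements said to be contradicted concern capture, recording, documenting and assessing. The disputed sentence concerns reports, and it stands directly above a table of submissions to the IRB and sponsor. On that reading nothing in Sections 2.9, 2.12 or the opening of 11.0 is switched off, and Section 2.14 still has the sponsor review every documented event.

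Part of this stands. A reader might infer that later events would be missing from the safety record, or that the rule cancels one of the two scheduled assessments. The protocol does not support either as a conclusion, because recording and sponsor review may well continue.

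The reply does not remove the conflict. Section 11.0 itself applies its severity grading to each event reported, so it does not keep the two words apart. If reports did mean only submissions to the IRB and sponsor, the stop would bear on exactly the serious and unanticipated events in the table. A subject-level stop there would be no safer.

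A second reply is that the paragraph is about following events to resolution, so the authors probably meant only to end reports on a resolved event. That may be so, but the text names the subject, and a centre should not have to guess.

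On causality, an event clearly due to the biopsy already fits *Not related*, and *Possible* also requires that other factors could explain the event. Misattribution is therefore confined to unclear cases. A reader might go further and call the lack of a separate rating for relatedness to biopsy or anaesthetic a defect. The documents do not support that: the CRF is not shown and may hold such a field, and serious events must reach the sponsor whatever that judgement is.

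**Conclusion.** The inconsistency is real and should be corrected. Section 11.0 contains a per-subject stop that disagrees with its own paragraph, its own opening sentence and Sections 2.9 and 2.12. It matters for one kind of event: a new one, most plausibly non-serious, that starts after all earlier study-associated events in that subject have resolved. Such an event could go unreported. Whether it would also go unrecorded depends on how centres read the sentence, so the size of the loss is uncertain. The bound is 10 subjects and 20 biopsy sites.

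A reader might infer that serious events could be suppressed. The 24-hour rule and the table entries are written without reference to the stop and stand on their own wording. No histological objective and no statistical figure is affected.

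The causality point is a minor wording inconsistency in one of five grades. It rests on reading sampling sessions as the biopsies.

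**What to change.** Delete the stop sentence from Section 11.0, or limit it to further reports on the same resolved event. Either change brings it into line with the rest of Section 11.0 and with Sections 2.9 and 2.12.

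In the same amendment, replace the reference to sampling sessions in *Possible* with investigational product, as in the neighbouring grades, so that a biopsy-type pattern alone does not meet a device-relatedness criterion. A separate rating of relatedness to the procedure is optional and not needed to resolve this point.

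The cost is two wording changes in one section, with the written IRB approval that Section 18.0 requires for any amendment. No visit, procedure or analysis changes.
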